4.6 Power Calculation

The full trial will be powered to detect a difference between the intervention and control group in our primary outcome: 6-month abstinence rate (see 4.5). Pooling results of the only three RCTs comparing e-cigarettes with placebo e-cigarettes [38, 39, 87] yields an expected effect size of OR 2.01 for 6-months abstinence rates. We consider this estimate to be conservative as most of these trials used older, less effective first-generation ecigarettes. In fact, a recently published trial comparing an active treatment (NRT) with a modern, third generation e-cigarette in the context of stop smoking services [41] found a superior effect of e-cigarettes on 6-months abstinence rates of OR 1.63. Based on established effect estimates for NRT vs placebo [88], findings from this trial therefore indirectly suggest that compared with placebo/usual care, third generation e-cigarettes (as will be used in this trial) may increase 6-months abstinence rates nearly three-fold (OR 2.85). Using the more conservative effect estimate of OR 2.01, we expect an absolute predicted risk difference of 6.7%, assuming 6-months abstinence rates in the control (standard care) group of 7.7% (based on EAGLES [67] and SCIMITAR-plus [30] trials which were conducted in PWMI) and 14.4% in the intervention (e-cigarette) group. A sample of 740 participants (370 per group) would provide 80% power, with alpha=0.05 in two-tailed analysis to detect this conservative effect. This sample size would also provide 95% power to detect a more likely effect of OR 2.43 (intermediary between the conservative and more optimistic effect), with an absolute predicted risk difference of 9.2% at 6 months (7.7% for control group vs 16.9% for treatment group).

4.7 Proposed analyses

Baseline characteristics will be reported by each arm using descriptive statistics.

4.7.1 Clinical effectiveness

Primary (CO-verified 7-day abstinence rates at 6-month follow-up) and other secondary binary outcomes will be analysed first by Fisher's exact test and then log-binomial regression adjusting for known predictors of cessation [89], comparing the intervention with the control group. Repeated measures analyses (e.g., mixed modelling, generalised linear models) will be used to analyse changes across baseline, 1- and 6-month follow-ups. Analyses of smoking-related outcomes will follow the intention-to-treat principle where those lost to follow-up are treated as smokers. Missing data for other outcomes will be explored to understand if they are missing at random, and appropriate approaches to dealing with missing data (e.g., multiple imputation) will be implemented, if necessary.

Relative risk and 95% confidence intervals will be calculated for all outcomes. As for Phase I, in the event of a non-significant difference between groups on primary and other outcomes, associated Bayes Factors will be calculated using the method of Dienes to differentiate between evidence for no effect from data insensitivity [74]. No subgroup analyses are planned due to limited power to detect effects. All analyses will be carried out by a statistician blinded to intervention allocation. Data will not be unblinded until the end of the study except for consideration of serious adverse events by the data management committee. A full data analysis plan will be developed and published prior to start of data collection on an appropriate trial register.

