3.4.2 Control group - Usual care

The control group will receive care as usual, as outlined above. As is common practice in pragmatic 'real-life' trials that involve variations of 'usual care' across organisations and localities, we will record the characteristics and details of usual care provided at each site to take these into account in the analyses and will codify treatment content in both groups using a well-established behaviour change taxonomy commonly used in tobacco research [52].

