3.5 Randomisation and allocation concealment

The intervention allocation will be determined by block computer-randomisation to ensure that each trial site has an equal proportion of intervention and control group participants. Those on the online pathway (pathway 1; see 3.6.3) will be informed electronically via email and those on the paper-based pathway (pathway 2; see 3.6.3) will

open a sealed envelope at their appointment. Randomisation will occur after consent to take part in the study has been obtained. Due to the nature of the intervention, it will not be possible to blind participants or all researchers to treatment allocation. The lead applicants, co-applicants, and statisticians, however, will be blinded.

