4.2 Design, Randomisation, Treatment groups

We intend to follow a similar approach to the feasibility trial (see Figure 1) for the design (including recruitment method), randomisation, intervention content and delivery in the full RCT, optimised based on findings from Phase I. There will be two main differences: expanded questionnaires to assess all secondary outcomes relevant for a full RCT (see 2.5), and the addition of a follow-up point at 6 months. We judged 6-months abstinence rates to be appropriate, as this is a follow-up period recommended by relevant Cochrane effectiveness reviews [37] and trial guidelines [77]. While the Phase I feasibility trial assessed abstinence at an earlier time point, relapse rates for smoking cessation treatments from one month onwards are relatively stable [78]. Therefore, it can be assumed that if the 1-month abstinence rate observed in the feasibility trial is promising (as assessed by confidence interval approach and Bayes Factor analysis), this will translate into meaningful group differences at 6-month follow-up.

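### Primary outcome: Fisher's exact test ignores the site blocking and uses only about 3.7% of its 5%; a single site-stratified decision analysis would be a free improvement

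*Protocol*

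**What the plan says.** Protocol section 4.7.1 covers the primary outcome (CO-verified seven-day abstinence at six months) and the other binary outcomes. They are analysed first by Fisher's "exact test and then log-binomial regression adjusting for known predictors of cessation [89], comparing the intervention with the control group". The section asks for relative risks with 95% confidence intervals, promises a full analysis plan before data collection, and does not mention site.

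Section 3.5 (Phase I) uses "block computer-randomisation to ensure that each trial site has an equal proportion of intervention and control group participants". Section 4.2 extends this to Phase II: "We intend to follow a similar approach to the feasibility trial (see Figure 1) for the design (including recruitment method), randomisation".

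Section 3.4.2, also in the Phase I part, expects usual care to vary between places and says "we will record the characteristics and details of usual care provided at each site to take these into account in the analyses".

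Section 4.6 gives the sample size: "A sample of 740 participants (370 per group) would provide 80% power, with alpha=0.05 in two-tailed analysis". It rests on "assuming 6-months abstinence rates in the control (standard care) group of 7.7" per cent and "14.4% in the intervention (e-cigarette) group". A second scenario follows: "This sample size would also provide 95% power to detect a more likely effect of OR 2.43".

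**The concern.** Site is used to balance the arms, and the protocol expects sites to differ in usual care. The first analysis listed for the primary outcome nevertheless pools all sites, and Fisher's test has no way to take a stratum into account. When arms are balanced within strata that differ in outcome, an unstratified test overstates the variance of the treatment contrast. Fisher's test adds its own conservatism, because its attainable p-values are discrete and it is calibrated on fixed margins. Both effects lower the real significance level below 5% and give away some power.

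A smaller point is that two analyses are listed in sequence, one unadjusted and one adjusted, and neither is called decisive. Section 4.7.1 makes the Bayes factors conditional on a non-significant result, so it presupposes a single verdict.

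**Working it through.** **Inputs.** From section 4.6: 370 per arm, two-sided alpha 0.05, p1 = 0.077, p2 = 0.144, difference d = 0.067. From section 4.4: three existing Trusts plus at least two more, with three sites each, so about 5 × 3 = 15 sites. The protocol gives no figure for between-site variation. I assume a normal site effect on the log-odds with SD 0 to 1.0.

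**1. The plan's own figure.** With mean rate p̄ = 0.1105:

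n = [1.960·√(2·p̄(1−p̄)) + 0.842·√(p1(1−p1) + p2(1−p2))]² / d² = (0.869 + 0.371)² / 0.004489 ≈ 343 per arm.

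With continuity correction: n/4 · [1 + √(1 + 4/(n·d))]² = 85.63 × (1 + 1.0837)² ≈ 372 per arm.

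The stated 370 therefore fits a continuity-corrected or Fisher calculation, and the figure is reproduced.

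**2. Exact size and power at 370 per arm**, by summing binomial probabilities over every pair of counts that each test rejects:

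| True rates | Fisher | Pearson chi-square |
|---|---|---|
| 7.7% in both (size) | 3.66% | 4.94% |
| 11% in both (size) | 3.78% | 4.99% |
| 14.4% in both (size) | 3.94% | 4.97% |
| 7.7% vs 14.4% (power) | 80.4% | 83.5% |
| 7.7% vs 16.9% (power) | 96.4% | 97.2% |

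Fisher meets both stated powers (80% and 95%). Leaving Fisher is worth 83.5 − 80.4 = 3.1 points before site is considered.

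**3. Adding site.** I simulated 740 participants in 15 sites (ten of 50 and five of 48, split 1:1 within site), with 60,000 trials per setting. The overall rates were held at the protocol's 7.7% and 14.4%. The simulation error on power is about 0.16 points.

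| Site SD (assumed) | Fisher power | Pearson power | Site-stratified Mantel-Haenszel power | Gain over Fisher | Of which stratification | Size: Fisher / Mantel-Haenszel |
|---|---|---|---|---|---|---|
| 0 | 80.6% | 83.6% | 83.6% | 3.0 | 0.0 | 3.6% / 4.8% |
| 0.3 | 80.0% | 83.2% | 83.4% | 3.4 | 0.2 | 3.6% / 5.0% |
| 0.5 | 80.5% | 83.5% | 84.0% | 3.5 | 0.5 | 3.5% / 4.9% |
| 0.8 | 80.8% | 84.0% | 85.4% | 4.5 | 1.4 | 3.2% / 5.0% |
| 1.0 | 81.1% | 84.2% | 86.1% | 5.0 | 2.0 | 3.0% / 4.9% |

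Other reasonable set-ups (5 or 15 strata, or 7.7% placed at the median site) move these gains a little. Across them the range is about 3 to 6 points over Fisher, of which about 0 to 2.5 points come from stratification.

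**4. How often the two listed analyses disagree at 0.05.** For Fisher against an unadjusted log-binomial test, they disagree in 2.8% of trials at the design effect and 1.0% under the null. Against a log-binomial model with one assumed three-level predictor (relative risk 1.0 to 2.0 per level), the figures are about 2.5 to 5.5% and 0.9 to 2.0%.

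**The case against.** The strongest reply is that nothing here is invalid. Fisher's test protects type I error, and the sample size was evidently computed to suit it, so test and sample size agree. Preferring another valid test could be called taste. Covariates, stratification terms and the choice of decisive analysis are often left to the analysis plan, which section 4.7.1 promises. Much of this stands, and it is why the point is graded low. It does not remove the point, because 4.7.1 does state a specific unstratified test for a site-blocked design, and a better one costs nothing.

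Three stronger readings are tempting, and the document does not support them.

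- A reader might infer that the regression leaves site out. The protocol does not say so. It cites a source for established predictors of quitting without listing them, and section 3.4.2 says site-level usual care will be taken into account. Silence in 4.7.1 is not exclusion.
- A reader might infer that ignoring site pulls Fisher below 80%. Simulated powers of about 76, 73 and 70% at site SD 0.5, 0.8 and 1.0 can be produced, but with 720 participants and the odds ratio of 2.01 fixed within site. The overall intervention rate then drops to about 14.2, 13.8 and 13.6%. That is a smaller effect than the planned 14.4%, and the stratified test loses power in the same set-up (80, 79 and 77%). At the protocol's own rates Fisher stays at about 79 to 81%.
- A reader might put the whole gain down to stratification. At SD 0.5 or below, stratification accounts for half a point or less.

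**Conclusion.** The point holds as a low-severity, cost-free improvement. The first-listed primary analysis is an unstratified Fisher's exact test in a trial blocked by site. It runs at a true size of about 3.7% (3.66% to 3.94% over common rates from 7.7% to 14.4%), and lower if sites differ. A site-stratified Mantel-Haenszel test restores the size to about 5% and raises power by about 3 to 6 points, mainly through leaving Fisher.

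The exact figures rest only on the protocol's rates and sample size. The stratification share rests on the assumed site SD of 0 to 1.0 and about 15 near-equal sites. There is no type I inflation and no deficit against the stated 80%. The missing rule on which analysis decides is minor: it would matter in roughly 1 to 5.5% of trials, and taken alone it could be left to the analysis plan.

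**What to change.** In section 4.7.1, name one decision analysis for the primary outcome that includes the blocking factor. Either of these would serve:

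- a site-stratified Mantel-Haenszel test, reported with a relative risk and 95% confidence interval; or
- the log-binomial model with site plus the listed baseline predictors, with modified Poisson regression and robust standard errors if it does not converge.

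State that very small sites are grouped by Trust, and make Fisher's exact test supportive. The Bayes-factor step should then refer to the decision analysis.

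The cost is one or two sentences, with no new data and no change to the 740. The grouping rule should be fixed before any outcome is seen; the published analysis plan promised in 4.7.1 is the natural place for its detail.

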3.8 Measures

3.8.1 Baseline measures

Baseline measures will be collected via a brief questionnaire and health records.

- *3.8.1.1 Socio-demographic characteristics:* These include age, sex, employment status, ethnicity, education, employment, accommodation type and marital status.
- 3.8.1.2 Smoking-related characteristics: These include general smoking characteristics, quit attempts and methods (including e-cigarettes), nicotine dependence [53], strength of urges to smoke (SUTS) [54], motivation to quit [55] and adexhaled breath carbon-monoxide (CO) reading.
- 3.8.1.3 General and mental health-related characteristics: These include most recent diagnosis (if available), antipsychotic medication use, and acute events (e.g. hospitalisation) in the last year. Mental health symptoms will be assessed with the PHQ-9 [56], GAD-7 [57] and SF-12 questionnaires [58].
- 3.8.1.4 Health behaviour characteristics: Alcohol use [59], exercise [60] and diet [61] will be assessed.

3.8.2 Primary outcome measures:

3.8.2.1 Feasibility and acceptability outcomes: The primary feasibility outcome measures in the feasibility trial will be consenting rate and recruitment frequency. Consenting rate will be calculated from the number of eligible participants approached who consent to take part in the study. The criterion to judge whether a large-scale RCT is feasible using the proposed recruitment approach is consenting a minimum of ~15% of eligible participants (see 3.14) which is slightly lower than the consenting rate typical in clinical trials in general patient populations in the UK [62]. Recruitment frequency will be calculated as the number of eligible patients at each site who agree to participate in the trial per month. Based on our projection of the number of participating trusts and sites in the full RCT, we would require around six participants per month from each Trust to deliver the full RCT successfully (see 3.9/4.4). MHR (or CPN) will be asked to record the number of non-eligible patients using a check list of common reasons for exclusions.

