3.10 Analyses

The results of the feasibility trial (e.g., preliminary effectiveness, feasibility and acceptability) will determine whether a full RCT (Phase II) is viable. The primary outcome, smoking abstinence for weeks 2-4 from enrolment or target quit date (for those who set a date within one week of enrolment), assessed at 1-month follow-up will be descriptively analysed in line with the one-sided confidence interval approach [47]. Consenting rate, recruitment frequency as well as attrition and adherence rate will be calculated to determine feasibility and to decide which recruitment route is most effective. Qualitative data on acceptability will be analysed using Framework analysis, guided by the Theoretical Framework of Intervention Acceptability [63], to determine themes related to barriers and facilitators to intervention acceptability, and with thematic analysis [73] to explore interview data from trial participants and research and CMHT or allied mental health professional staff. We will also conduct a simple cost effectiveness analysis to determine incremental cost-effectiveness ratios for each additional quitter in the intervention compared with control group. Secondary clinical outcome measures will be analysed using generalised linear models (with intervention allocation specified as between-group factor and time as within-group factor) to determine reductions in cigarette consumption and exhaled breath carbon-monoxide readings and changes in mental health measures from baseline to 1-month follow-up. Fidelity will be determined using an established methodology of BCT-coded audio recording of intervention sessions [66]. Finally, for all quantitative analyses (primary and secondary outcome measures), Bayes Factors will be calculated to examine for non-significant results whether the associations indicated evidence of no effect or data being insensitive to detect an effect, and for significant results, the strength of evidence [74].

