4.5.2 Secondary outcome measures

- 4.5.2.1 Clinical (smoking-related) outcomes: At one month, self-reported and CO-verified smoking abstinence rates, 2-4 weeks from enrolment or target quit date (whichever is later) will be recorded. Continuous abstinence at 6-month follow-up will be defined as not having had more than 5 cigarettes between two weeks after enrolment and follow-up, in line with Russell standards [77]. Unsuccessful quit attempts in the past six months will also be recorded. In line with the feasibility trial, smoking reduction in cigarette consumption by 50% or in CO reading by 30% will be assessed at both 1- and 6-month follow-up.
- 4.5.2.2 Clinical (mental health-related) outcomes: At 6-month follow-up only, general and mental health functioning will be assessed using measures detailed in 3.8.1.3.
- 4.5.2.3 Practical (design-related) outcomes: As in Phase I, attrition and, in the intervention group, adherence rate will be assessed at 1-month follow-up. Attrition will also be assessed at 6-months follow-up, in addition to continued use of e-cigarettes in the intervention group and de novo e-cigarettes use in the control group.
- 4.5.2.4 Psychosocial outcomes: Health-related quality of life will be assessed using EQ-5D-5L [82] and the mental health specific ReQoL [83] at final follow-up. Health and social care service use will be measured using the Client Service Receipt Inventory (CSRI), which has been validated against objective primary care records [84] and is also recommended for usage of hospital and other community health services [85]. Changes from baseline in other health behaviours (see 3.8.1.4) will be determined at 6-month follow-up.
- 4.5.2.5 Cost effectiveness: To determine short-term cost-effectiveness of the intervention, we will undertake a within-trial incremental cost-effectiveness analysis to assess the value

for money afforded by the intervention over and above the usual care using data collected during the trial. A service use questionnaire piloted in the feasibility workstream will be used to collect resource use at baseline, one and six months and will include both the cost of providing the interventions and the costs of patients' health care utilisation from an NHS perspective as recommended by NICE technology appraisal guide [86]. To assess long-term cost, effectiveness, we will undertake economic modelling (see 4.7).

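### Continuous secondary outcomes are compared with baseline as one of the outcome times and no stated baseline adjustment, which loses precision if the baseline means are left free

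*Protocol*

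**What the plan says.** Protocol 3.10 (Phase I) analyses the secondary clinical outcomes with generalised linear models, "with intervention allocation specified as between-group factor and time as within-group factor", to describe reductions in cigarettes and CO and changes in mental health measures from baseline to 1 month. Protocol 4.7.1 (Phase II) says "Repeated measures analyses (e.g., mixed modelling, generalised linear models) will be used to analyse changes across baseline, 1- and 6-month follow-ups". Neither section mentions the baseline score as a covariate or a common baseline mean. By contrast, 4.7.1 states covariate adjustment for binary outcomes, which are "analysed first by Fisher's exact test and then log-binomial regression adjusting for known predictors of cessation".

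The baseline scores are available. In 3.8.1, "Mental health symptoms will be assessed with the PHQ-9 [56], GAD-7 [57] and SF-12 questionnaires", and alcohol use, exercise, diet, smoking characteristics and a CO reading are also taken. Follow-up is sparse: Phase I has one visit at 1 month, and in Phase II "At 6-month follow-up only, general and mental health functioning will be assessed using measures detailed in 3.8.1.3" (4.5.2.2). For health behaviours, "Changes from baseline in other health behaviours (see 3.8.1.4) will be determined at 6-month follow-up" (4.5.2.4).

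Three outcome groups differ:
- Quality of life: "Health-related quality of life will be assessed using EQ-5D-5L [82] and the mental health specific ReQoL [83] at final follow-up"; neither instrument is in the baseline list of 3.8.1.
- Phase II smoking reduction is defined by thresholds: "smoking reduction in cigarette consumption by 50% or in CO reading by 30% will be assessed at both 1- and 6-month follow-up".
- CO: 3.6.3 reserves in-person follow-up for confirming reported abstinence, although 3.8.3.2 plans a CO change in both Phase I arms.

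**The concern.** A model with group and time as crossed factors treats the baseline score as a response. With two time points and baseline means free to differ between arms, its group-by-time test is the test on change scores. Randomisation makes the true baseline means equal, so estimating a separate baseline mean in each arm spends information for nothing. Adjusting the follow-up value for baseline is also unbiased and, apart from one degree of freedom, at least as precise.

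At stake is the width of the confidence intervals for the between-arm effects on mental health scores, health behaviours and, in Phase I, cigarettes per day. The mental health scores matter most: they show whether the intervention affects symptoms in this population, and the protocol states no power for them.

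**Working it through.** **The plan's own figure.** The protocol gives no power or precision for a between-arm comparison of any continuous outcome. The one Phase II figure, 740 participants (370 per group) for 7.7% against 14.4% at two-sided 0.05, is for the binary primary outcome. Fisher's exact test at 370 per group has power 80.4%, which matches the stated 80%. It does not depend on this point.

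**Inputs.** Group sizes are 36 (3.9) and 370 (4.6). Attrition of 30% is the ceiling set in 3.8.2.1 and 3.13; it is used here only to illustrate 370 × 0.7 = 259 per group. The correlation r between baseline and follow-up is an assumption, shown over a range. Variances at the two times are assumed equal.

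**Formulas.** In units of the outcome variance, and apart from the common factor 2/n:
- change score: 2(1 − r)
- adjusted for baseline: 1 − r²
- ratio of adjusted to change: (1 + r)/2
- precision lost by the change score: 1 − (1 + r)/2 = (1 − r)/2

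| Assumed r | Change score | Adjusted | Precision lost | Standard error inflated by |
|---|---|---|---|---|
| 0.2 | 1.60 | 0.96 | 40% | 29.1% |
| 0.3 | 1.40 | 0.91 | 35% | 24.0% |
| 0.5 | 1.00 | 0.75 | 25% | 15.5% |
| 0.6 | 0.80 | 0.64 | 20% | 11.8% |
| 0.7 | 0.60 | 0.51 | 15% | 8.5% |
| 0.9 | 0.20 | 0.19 | 5% | 2.6% |

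For r of 0.5 to 0.7 the change score needs 1/0.75 = 1.33 to 1/0.85 = 1.18 times as many participants for the same precision.

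**Difference detectable with 80% power**, (1.96 + 0.84) × √(2v/n) in SD units, where v is the table entry, with a normal approximation and complete data in n per group:

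| n per group | r = 0.5, change / adjusted | r = 0.7, change / adjusted |
|---|---|---|
| 36 | 0.66 / 0.57 | 0.51 / 0.47 |
| 370 | 0.206 / 0.178 | 0.160 / 0.147 |
| 259 | 0.246 / 0.213 | 0.191 / 0.176 |

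**Three-visit mixed model.** The generalised least squares variance of the 6-month effect (baseline, 1 and 6 months, one common correlation, complete data) gives the same answers. With free baseline means it is 1.00 at r = 0.5 and 0.60 at r = 0.7, equal to the change score. With a common baseline mean it is 0.75 and 0.51, equal to baseline adjustment. The loss thus comes from leaving the baseline means free, not from using a mixed model.

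**Unequal variances.** If the follow-up SD is k times the baseline SD, the variances are 1 + k² − 2rk and k²(1 − r²). Their difference is (1 − rk)², which is never negative. The size of the loss depends on k, but its direction does not.

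**The case against.** The strongest objection is that Phase II does not fix the analysis. Section 4.7.1 names model classes only as examples, does not exclude a baseline covariate and defers detail to a full data analysis plan. A mixed model with a common baseline mean fits its wording and loses nothing. This stands for Phase II: a reader might infer that the protocol rejects baseline adjustment there, and the text does not say so. It does not dispose of 3.10, which states the between-by-within layout and carries no such deferral.

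Second, Phase I is powered in 3.9 for within-subject reductions in cigarettes and CO, and time as a within factor serves that aim. Regression of the follow-up value alone would not deliver the within-arm change. This also stands: adjustment should be added for the between-arm comparison and should not replace the within-arm summary.

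Third, the reach is limited. Phase II cigarette and CO reduction are binary and fall under the covariate-adjusted analysis. Follow-up CO may be missing for most participants under 3.6.3. EQ-5D-5L and ReQoL have no stated baseline. The point therefore does not cover every secondary outcome.

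Fourth, the protocol gives no r, and equal variances are doubtful for cigarettes per day, because 3.9 expects half of the intervention arm to halve consumption. Any percentage is conditional.

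**Conclusion.** The point holds as an efficiency matter on secondary outcomes. Section 3.10 specifies, and 4.7.1 appears to continue, an analysis whose between-arm contrast is a change-score comparison when baseline means are left free. The cost is (1 − r)/2 of the precision: 25% to 15% if r is 0.5 to 0.7, and 40% to 5% over r of 0.2 to 0.9, given equal variances. It is zero if a common baseline mean is fitted.

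It applies to PHQ-9, GAD-7 and SF-12 in both phases, to continuous health-behaviour scores in Phase II, and to cigarettes per day in Phase I.

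A reader might go further and infer a biased analysis, an underpowered trial or a certain loss of 15–25%. The documents support none of these. Both contrasts are unbiased under randomisation. The primary outcome and the 740 sample size are binary, and the stop/go criteria in 3.13 do not use these comparisons. The percentage rests on a correlation that the protocol does not give.

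**What to change.** In 3.10 and 4.7.1, state that for each continuous outcome measured at baseline the arms are compared on the follow-up value adjusted for baseline. Either enter baseline as a covariate or fit a mixed model with a common baseline mean across arms. Report the adjusted mean difference with its 95% confidence interval.

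Keep the within-arm change from baseline as a separate summary, because Phase I is powered for it. Leave out EQ-5D-5L and ReQoL unless they are measured at baseline, and leave out the Phase II 50% and 30% reduction outcomes, which are binary. Include CO only where a follow-up reading is taken in all participants.

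The cost is a sentence in each section and one degree of freedom per model. No new data or participants are needed.
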